8. STATISTICAL METHODS AND DATA ANALYSIS

8.1. GENERAL STATISTICAL CONSIDERATIONS

A detailed statistical analysis plan (SAP) will be finalized before database lock and will document the analysis methods, data handling procedures, the handling of missing data, and other statistical analysis issues. Statistical analyses will be performed using SAS® software version 9.4 or higher. Data for Part 1, Part 2 Stage 1, and Part 2 Stage 2 will be analyzed separately.

8.2. DETERMINATION OF SAMPLE SIZE

Approximately 28 subjects will be randomized 1:1:1:1 into 4 dose cohorts (Formulation A) in Part 1, including up to 4 subjects who are non-evaluable per modified IWG-MRT-ECNM response criteria based on lack of evaluable organ damage per modified IWG-MRT-ECNM criteria. It was determined that approximately 6 subjects evaluable per modified IWG-MRT-ECNM response criteria per group (24 total) would allow for ruling out an ORR of 60% or higher if a dose group had an ORR estimate of 16.7% or less (ie, if the ORR for a dose is 1/6, the upper bound of the 1-sided 90% confidence interval is 51.0% via a Clopper-Pearson exact confidence interval). Dose decisions will be based on an assessment of safety, biomarker, and clinical efficacy, and PK endpoints at each dose, with summary statistics and figures being used to illustrate dose-response.

Part 2 of the study will enroll approximately 75 subjects who are evaluable per modified IWG-MRT-ECNM criteria and up to an additional 15 subjects with AdvSM who are non-evaluable per modified IWG-MRT-ECNM response criteria at study entry.

For Part 2 Stage 1, approximately 20 subjects who are evaluable per modified IWG-MRT-ECNM will be randomized in a 1:1 ratio to receive bezuclastinib 150 mg QD or 300 mg QD (Formulation B). It was determined that approximately 10 subjects evaluable per modified IWG-MRT-ECNM response criteria per group would allow for ruling out an ORR of 60% or higher if a dose group had an ORR estimate of 30.0% or less (ie, if the ORR for a dose is 3/10, the upper bound of the 1-sided 90% confidence interval is 55.2% via a Clopper-Pearson exact confidence interval). The determination of the optimal dose will be based on totality of the data including assessment of safety, biomarker and clinical efficacy, and PK endpoints at each dose level.

For Part 2 Stage 2, approximately 55 subjects who are evaluable per modified IWG-MRT-ECNM response criteria will be enrolled. The null hypothesis is that ORR for subjects who received bezuclastinib treatment will be the same as the historical control (28%) (RYDAPT SmPC, 2021). Assuming the ORR for subjects who received bezuclastinib is 60%, 55 evaluable subjects will provide at least 90% power to reject the null hypothesis based on a Chi square test at one-sided alpha of 0.025.

Once approximately 20 subjects have been enrolled in Part 2 Stage 1, enrollment may continue until the dose for Part 2 Stage 2 is confirmed. Following enrollment of 20 subjects in Part 2 Stage 1 and prior to analysis of Part 2 Stage 2 data, enrolled subjects will receive either 150 mg

and/or 300 mg based on ongoing review of available data and following IDMC approval. Of the additional subjects who may be enrolled, those who receive the dose selected for Part 2 Stage 2 will contribute to the Stage 2 analysis population.

The inclusion of up to 4 subjects in Part 1 and up to approximately 15 additional subjects in Part 2 Stage 2 who are non-evaluable per modified IWG-MRT-ECNM is intended to provide a broader understanding of efficacy including subjects with AdvSM without evaluable organ damage at baseline.

8.3. MULTIPLICITY ADJUSTMENTS

There is no multiplicity adjustment planned for this study.

8.4. ANALYSIS SETS

Analysis sets will be defined for each part and stage and for evaluable and non-evaluable subjects separately.

8.4.1. Screened Population

The Screened Population will include all subjects who sign informed consent.

8.4.2. Intent-to-Treat Analysis Set

For Part 1 and Part 2 Stage 1, the Intent-to-Treat (ITT) Analysis Set will include all randomized subjects.

For Part 2 Stage 2, the ITT Analysis Set will include all subjects who received study drug.

The ITT Analysis Set will be the primary population for efficacy analysis.

8.4.3. Modified ITT Analysis Set

The Modified ITT Analysis Set will include all ITT subjects who received at least 1 dose of bezuclastinib and had at least 1 post-baseline response assessment.

8.4.4. Response-Evaluable Analysis Set

The Response-Evaluable Analysis Set includes subjects who are evaluable per modified IWG-MRT-ECNM criteria who enrolled in the study at least 20 weeks before the data cutoff, ie, all subjects enrolled within 20 weeks will be excluded from the analysis regardless of study discontinuation status. The minimum required follow up time to observe a confirmed response is 20 weeks. This analysis set will be used when not all subjects have been followed long enough to observe a confirmed response.

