This is a 2-part study of the KIT inhibitor bezuclastinib in subjects with AdvSM. Part 1 will determine a clinically active and tolerable exposure range of bezuclastinib for subjects with AdvSM using the original bezuclastinib formulation (Formulation A). A modified formulation of bezuclastinib (Formulation B) has been developed with higher bioavailability. Formulation B will be introduced in Part 2, which will be conducted with a 2-stage design: Stage 1 will confirm the optimal dose of bezuclastinib Formulation B, and Stage 2 will consist of an expansion period. Patient eligibility will be reviewed and enrollment approved by an Eligibility Committee (EC) during the Screening Period. In addition, eligibility will be reviewed and confirmed by a retrospective EC, and disease response will be adjudicated by the CRRC. The Study Steering Committee (SSC) and the Sponsor will review all available data, including safety, efficacy, PK/pharmacodynamic, and dose modification data, from Part 1 after all subjects in Part 1 have been enrolled and completed at least 2 cycles of bezuclastinib Formulation A and from Part 2 Stage 1 after all subjects have been enrolled and completed at least 2 cycles of bezuclastinib Formulation B.

Throughout the study, oral bezuclastinib will be administered daily as a single agent. Each 28-day period is 1 cycle. Treatment will be continuous; there will be no gaps between cycles.

Part 1: Dose Optimization

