(a) After 15 cycles, dispensation of study drug for at-home administration and study drug diary will be adjusted accordingly.

(b) At C15 and beyond, and at most other study visits, clinical chemistry, hematology, pregnancy testing (women of childbearing potential only), AE monitoring, and collection of concomitant medications will be performed.

(c) EOT assessments should be performed within 7 days of decision to permanently discontinue study treatment.

(d) Subjects should be dosed as soon as possible after randomization and preferably within 7 days before receiving their first dose on C1D1.

(e) A complete PE will be performed at Screening only. At all other study visits, a targeted PE will be performed based on Investigator’s judgment and careful evaluation of the subject’s signs and symptoms.

- (f) Height at Screening only.
- (g) A single 12-lead ECG will be performed after the subject has been resting in supine or semi-supine position for at least 5 minutes. At all predose and postdose intervals, each ECG should occur just prior to each PK blood sample collection.
- (h) On C1D1 and C2D1, a single ECG will be performed predose (within 30 min prior to dosing) and at 1 (\pm 5 minutes), 3 (\pm 15 minutes), 5 (\pm 15 minutes), and 8 (\pm 30 minutes) hours postdose.
- (i) Safety laboratory tests (hematology, chemistry) may be completed 1 day prior to the visit on C1D1 (after randomization) or on C2D1.
- (j) Serum tryptase will be collected as indicated and at all response time points. Serum tryptase will be tested locally. A blood sample will also be collected and tested at a central laboratory. Additional exploratory analyses may be performed on blood samples to further explore pharmacodynamic markers in subjects with AdvSM.
- (k) Subjects with a positive HCV antibody may be eligible if HCV RNA is undetectable on a quantitative HCV RNA assay, following discussion with the Medical Monitor.
- (l) Women of childbearing potential only. A serum pregnancy test (β -human chorionic gonadotropin) will be performed at Screening, and a urine pregnancy test will be performed at subsequent visits.
- (m) QOL assessments to include Patient Global Impression of Severity (PGIS), Patient Global Impression of Change (PGIC), and the Mastocytosis Quality of Life Questionnaire (MC-QoL). PGIC will be performed starting on C2D1.

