3.1.4. Response Assessments

A bone marrow assessment will be performed on Cycle 3 Day 1 to document initial response. Bone marrow assessments will be performed every 3 cycles (approximately every 12 weeks) from Cycle 6 until Cycle 12 (Day 1 of C6, C9, C12), and then every 6 cycles (C18, C24, etc.) thereafter. If an initial response (CR, CRh, PR, or CI) is achieved on or after C12, a repeat bone marrow assessment will be performed 12 weeks after the initial documented response to confirm response per modified IWG-MRT-ECNM response criteria. Changes in liver and spleen size will be assessed by MRI and palpation. A computed tomography scan may be used if MRI cannot be performed. Skeletal imaging is required at Screening for all subjects to assess for baseline lytic lesions and/or pathologic fractures. Changes in the size of bony lesions will be assessed with skeletal imaging. Refer to [Section 6.15](#) for further information regarding disease assessments.

[figure not shown]

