6.3. ENROLLMENT

Enrollment will take place before the start of study drug administration. Once a subject has given written informed consent, the Investigator will commence all screening assessments. An Interactive Response Technology (IRT) system will be used for enrollment, randomization (in Part 1 and Part 2 Stage 1), and drug management. After all screening assessments have been completed and the EC has approved enrollment into the study, the IRT will assign each subject a Subject Identification Code.

The diagnosis and evidence of measurable disease must be evaluable according to response criteria and confirmed by the EC prior to randomization in Part 1 and Part 2 Stage 1 and prior to the first dose of study drug in Part 2 Stage 2. The EC will consist of a pathologist and at least 1 clinician who is skilled in the diagnosis and treatment of mastocytosis. The requirement for measurable disease is intended to ensure the eligibility of all subjects in Part 1 and Part 2 who are evaluable for response per modified IWG-MRT-ECNM criteria. The study allows for a subset of subjects in both Part 1 and Part 2 with AdvSM who are not evaluable per modified IWG-MRT-ECNM response criteria based on a lack of evaluable organ damage.

Subjects can be rescreened up to 2 times, at a maximum total of 3 screens, each screen consisting of all screening assessments and EC review.

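### The 20-week entry rule for the supplementary Response-Evaluable set runs from enrollment and uses the earliest possible confirmation time, so confirmed ORR on that set reads low at an early cutoff

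*Protocol*

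**What the plan says.** Section 8.4.4 admits subjects who are evaluable under the modified response criteria and were "enrolled in the study at least 20 weeks before the data cutoff". It gives the reason for the threshold, "The minimum required follow up time to observe a confirmed response is 20 weeks", and the use: "This analysis set will be used when not all subjects have been followed long enough to observe a confirmed response".

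The calendar comes from elsewhere in the Protocol. The Synopsis and Section 3.1 fix the cycle length: "Each 28-day period is 1 cycle". Section 3.1.4 sets the first assessment, "A bone marrow assessment will be performed on Cycle 3 Day 1 to document initial response", and then assessments "every 3 cycles (approximately every 12 weeks) from Cycle 6 until Cycle 12". Section 6.15.1 calls for a repeat marrow 12 weeks after a first documented response. Under Appendix D, a response held for less than 12 weeks does not qualify as CR, PR or CI. Section 8.7 counts only confirmed responders in ORR.

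On timing of entry, Section 6.3 says: "Enrollment will take place before the start of study drug administration". Table 1, footnote (d), adds: "Subjects should be dosed as soon as possible after randomization and preferably within 7 days before receiving their first dose on C1D1". Table 1 allows ±3 days for visits in Cycles 3 to 15.

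Sections 8.4.2 and 8.7 make the ITT set, not this one, the primary efficacy population.

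**The concern.** A maturity rule of this kind should keep out subjects who have not yet had the chance to be counted as responders. Section 8.4.4 falls short in two ways.

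First, the clock starts at enrollment, while the assessments run from first dose. A subject who only just qualifies may not have had the C6D1 visit at which even the earliest response is confirmed.

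Second, the shortest possible time to confirmation serves as the entry threshold. A subject in an ongoing response first documented at C6D1 enters the denominator but cannot enter the numerator until 12 weeks later. Section 8.4.4 does not set such pending responses apart.

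An early confirmed ORR on this set would therefore depend partly on how fast subjects were accrued and when the data were cut. A reader who compared it with the 60% planning assumption or the 28% reference in Section 8.2 would see a rate that is too low for reasons unrelated to the drug.

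**Working it through.** **Inputs from the Protocol.** Cycle of 28 days (Synopsis, Section 3.1). Assessments on Day 1 of C3, C6, C9 and C12 (Section 3.1.4, Table 3). Confirmation after 12 weeks (Section 6.15.1, Appendix D). Visit window of ±3 days for Cycles 3 to 15 (Table 1). Preferred gap from randomization to first dose of up to 7 days (Table 1, footnote d). Planning ORR of 60% (Section 8.2).

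**1. Reproducing the 20 weeks.** Week of Day 1 of cycle k = (k − 1) × 28 / 7. Earliest confirmation = that week + 12.

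| First documented at | Week from first dose | Earliest confirmation |
|---|---|---|
| C3D1 | 8 | 20 |
| C6D1 | 20 | 32 |
| C9D1 | 32 | 44 |
| C12D1 | 44 | 56 |

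The stated 20 weeks reproduces. It is the first row only, and it is measured from first dose.

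**2. The same visit measured from enrollment.** C6D1 is day 140 after first dose.
- No gap, visit 3 days late: (140 + 3) / 7 = 20.4 weeks.
- 7-day gap, visit on time: (7 + 140) / 7 = 21.0 weeks.
- 7-day gap, visit 3 days late: (7 + 140 + 3) / 7 = 21.4 weeks.

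In each case a subject at exactly 20 weeks from enrollment qualifies for the set before the confirming visit. The 7 days is a preference, not a limit, so a longer gap adds to this.

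**3. Illustrating the size of the bias.** The Protocol gives neither an accrual plan nor a distribution of time to response, so both are assumed:
- accrual is uniform and still running, with the cutoff 52 weeks after first enrollment;
- a fraction f of eventual responders is first documented at C6D1 and the rest at C3D1;
- the enrollment-to-dose gap is ignored.

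At that cutoff the set holds subjects with 20 to 52 weeks of follow-up, a span of 32 weeks. The share with less than 32 weeks is (32 − 20) / (52 − 20) = 12 / 32 = 37.5%.

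Expected confirmed ORR = 0.60 × (1 − f × 0.375):
- f = 0.20: 0.60 × 0.925 = 0.555, or 55.5%, a loss of 4.5 points.
- f = 0.35: 0.60 × 0.86875 = 0.521, or 52.1%, a loss of 7.9 points.
- f = 0.50: 0.60 × 0.8125 = 0.4875, or about 48.8%, a loss of about 11.3 points.

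First responses at C9 or later are left out. Including them would increase the loss, because they need 44 weeks or more.

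**The case against.** **The set is not primary.** This stands. A reader might infer that the Stage 2 test against 28% is biased by this rule. The documents do not support that: Sections 8.4.2 and 8.7 place the primary ORR analysis on ITT, and nothing ties the test to the Response-Evaluable set. At the same immature cutoff ITT would be at least as affected, since it also includes subjects with less than 20 weeks. In that respect the set reduces the problem without removing it.

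**The figure is correct as stated.** It is called a minimum, and counted from first dose it is one. What does not stand is applying it from enrollment, where it falls short of that minimum, or treating it as enough follow-up for every included subject.

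**The wrong cutoff can exaggerate the effect.** It is tempting to compute the under-32-week share at the moment the last subject reaches 20 weeks. By then the rule excludes no evaluable subject, so the set is doing no work. Only a cutoff during accrual or soon after it is relevant, hence the choice of illustration.

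**Some responses may be dated between marrow visits.** This stands in part. Clinical improvement can rest on laboratory values (Appendix C), hematology and chemistry are scheduled every cycle, and Table 3 allows response assessment when clinically indicated. If onset may be dated at C4 or C5, 12 weeks are complete at week 24 or 28. So it goes too far to say that before week 32 only a C3 responder can be confirmed. The claim holds for responses first documented at C6D1.

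**The bias is conservative, and the clock error is small.** Both stand. A downward bias does not inflate false-positive claims. The clock error is about 1.4 weeks with a 7-day gap. Footnote (d) concerns randomization, and Stage 2 is not randomized, although Section 6.3 still places enrollment before dosing.

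**A longer threshold is also arbitrary.** This stands. A rule near 32 weeks still leaves C9 responders pending until week 44 and C12 responders until week 56. It is a trade-off and better suited to a sensitivity analysis.

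**Conclusion.** The point holds for the supplementary set at an immature cutoff. Counted from enrollment, 20 weeks does not guarantee the minimum follow-up that Section 8.4.4 claims: the confirming C6D1 visit can fall about 21.4 weeks after enrollment with a 7-day gap. Subjects with 20 to less than 32 weeks whose response is first documented at C6D1 count as non-responders while their confirmation is pending, so confirmed ORR on this set is biased low.

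That pending subjects count as non-responders is not stated in so many words. It follows from the confirmed-only numerator in Section 8.7 and the 12-week requirement in Appendix D.

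The direction is certain whenever such subjects are present; the size is not. The losses of 4.5 to about 11 points rest on assumed uniform accrual, a 52-week cutoff and 20% to 50% of responders first seen at C6. They illustrate an early look and do not predict the final ORR. The documents do not support a stronger claim about the primary analysis or type I error.

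**What to change.** In Section 8.4.4:

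1. Count follow-up from first dose and include the C6D1 window, for example first dose at least 20 weeks plus 3 days (143 days) before the data cutoff, regardless of discontinuation.
2. Label confirmed ORR on this set as preliminary.
3. Report unconfirmed responses awaiting confirmation separately. Appendix D already requires responses of less than 12 weeks to be recorded, so no new data are needed.
4. Optionally, add a sensitivity analysis limited to subjects whose first dose was at least 32 weeks plus the window before the cutoff.

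Item 1 repairs the clock. It does not remove the downward bias from pending C6 responses; items 2 and 3 make that visible.

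The cost is a slightly smaller set at an early cutoff and one extra table. In the 52-week illustration with a 7-day gap, entry moves from 140 to 150 days after enrollment, and the set shrinks by (10 / 7) / 32 = 4.5%. The optional analysis would leave out the 37.5% with less than 32 weeks, and slightly more once the window and gap are counted. No further subjects, visits or procedures are needed.

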8.4.5. Safety Analysis Set

The Safety Analysis Set will include all subjects who received at least 1 dose of bezuclastinib. This population will be used for all safety assessments.

8.4.6. Pharmacokinetic Analysis Set

The Pharmacokinetic Analysis Set will include all subjects who received at least 1 dose of bezuclastinib and have at least 1 measurable postdose concentration.

8.4.7. Pharmacodynamic Analysis Set

The Pharmacodynamic Analysis Set will include all subjects who received at least 1 dose of bezuclastinib and have at least 1 measurable postdose pharmacodynamic evaluation.

8.5. TREATMENT ASSIGNMENT, RANDOMIZATION, AND STRATIFICATION

Subjects in Part 1 will be randomized to receive bezuclastinib (Formulation A) in a 1:1:1:1 (50 mg BID:100 mg BID:200 mg BID:400 mg QD) manner. Randomization will be stratified by evaluability per modified IWG-MRT-ECNM response criteria (ie, evaluable vs non-evaluable).

Subjects in Part 2 Stage 1 will be randomized to receive bezuclastinib (Formulation B) in a 1:1 (150 mg QD:300 mg QD) manner. Randomization will be stratified by prior treatment with TKI (ie, yes vs no).

Subjects in Part 2 Stage 2 will receive bezuclastinib at the selected optimal dose based on data from Part 1 and Part 2 Stage 1.

8.6. BACKGROUND CHARACTERISTICS

8.6.1. Subject Disposition

The number and percentage of subjects in each disposition category (eg, enrolled, included in each analysis set, completing a given number of treatment cycles, discontinuing treatment, and discontinuing study, with a breakdown of the reasons for discontinuation) will be summarized by dose cohort.

8.6.2. Demographics and Baseline Characteristics

The following demographics and baseline characteristics will be summarized by dose cohort for the Safety Analysis Set: sex at birth, race, age at Screening, disease type (ASM, SM-AHN, or MCL), and ECOG performance status. These parameters will be summarized by incidence (n, %). Additional parameters may be specified in the SAP.

8.7. EFFICACY ANALYSES

The primary efficacy endpoint for subjects who are evaluable per modified IWG-MRT-ECNM response criteria is ORR, defined as the percentage of subjects classified as confirmed responders (CR, CRh, PR, or CI) according to the response assessment based on modified IWG-MRT-ECNM response criteria by CRRC assessment (see [Table 8](#)). Analysis of the primary efficacy endpoint will be performed on the ITT Analysis Set for Part 1, Part 2 Stage 1, and Part 2 Stage 2, separately. For the purposes of dose selection, subjects who had dose reductions will be treated as non-responders for their assigned dose arm as a sensitivity analysis. For each dose

group, summary statistics including the number and proportion of confirmed responders with 95% confidence intervals will be presented.

Other efficacy assessments include DOR, TTR, and PFS, based on modified IWG-MRT-ECNM, PPR, and OS. The endpoints based on modified IWG-MRT-ECNM response criteria will be summarized using the ITT Analysis Set. Sensitivity analysis for selected efficacy endpoint will be summarized using the mITT analysis set.

All efficacy endpoints will be summarized by study part/stage (Part 1, Part 2 Stage 1, and Part 2 Stage 2) and dose cohort. Efficacy endpoints will be listed as well. When appropriate, subjects across study parts and by disease subtype may also be grouped.

Table 8: Response Category for Responder Definition by Subject Type

Responder	Modified IWG-MRT-ECNM Criteria
Yes	Complete Remission (CR)
	Complete Remission with Incomplete Hematologic Recovery (CRh)
	Partial Remission (PR)
	Clinical Improvement (CI)
No	Stable Disease (SD)
	Progressive Disease
	Loss of Response
	Not Evaluable

Source: [Gotlib et al, 2013](#).

The summaries for the following endpoints will be provided along with 95% confidence intervals. Individual subject responses will also be represented using waterfall plots.

- Number (%) of subjects in each tumor response category
- Number (%) of subjects who met the Overall Responder definition (CR+CRh+PR+CI)
- Number (%) of subjects who met the Complete Remission criteria (CR+CRh)
- Number (%) of subjects who met the criteria for PPR

For Part 2 Stage 2, ORR will be tested against null hypothesis of response rate 0.28 using Chi square test at one-sided alpha of 0.025.

For the following endpoints, PFS and OS will be summarized using Kaplan-Meier Product-Limit survival analysis, including the estimates of 25%, 50%, and 75% percentiles and 95% confidence intervals, and DOR and TTR will be summarized with mean and standard error (if data warrant):

- DOR, defined as the time from the date of first CR, CRh, PR, or CI to the date of disease progression or death from any cause, whichever occurs first. DOR can only be determined in subjects who have CR, CRh, PR, or CI.

- TTR, defined as the time from the date of randomization/first dose of study drug until the first documented response (CR, CRh, PR, or CI). Time to best response will also be calculated.
- PFS, defined as the date of randomization/first dose of study drug to the date of first documented confirmed disease progression or death from any cause, whichever occurs first.
- OS, defined as the date of randomization/first dose of study drug to the date of death from any cause.

The following censoring rules will apply to subjects who survive at the end of the study:

- All subjects will be censored at the last date of study participation.
- Subjects who are lost to follow-up and subjects who discontinued study for any reason will be censored at the last date of contact.

An assessment of OS and PFS will be performed with and without censoring for subsequent therapy.

Changes in spleen and liver sizes will be assessed by MRI and palpation.

Evaluation of biomarkers of mutation burden and VAF in bone marrow or other samples as appropriate before and after treatment with bezuclastinib ex vivo. Potential biomarkers will be correlated with clinical outcomes.

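### Read as uncorrected, the Part 2 Stage 2 chi-square test exceeds its one-sided 0.025 level at the planned 55 subjects (exact size 0.0366)

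*Protocol*

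**What the plan says.** Section 8.7 fixes the method, null value and level: "ORR will be tested against null hypothesis of response rate 0.28 using Chi square test at one-sided alpha of 0.025". Section 8.2 takes the 28% from a historical control and assumes 60% on bezuclastinib. It claims that "55 evaluable subjects will provide at least 90% power to reject the null hypothesis based on a Chi square test" at the same one-sided level, and the sample size considerations in the synopsis say the same. None of the three places says whether the chi-square statistic is continuity-corrected or whether an exact version is meant.

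The sample size is approximate: "For Part 2 Stage 2, approximately 55 subjects who are evaluable per modified IWG-MRT-ECNM response criteria will be enrolled". Sections 3.1.3 and 8.2 also let some subjects enrolled after the first 20 of Stage 1 join the Stage 2 analysis population, if they received the dose that is later selected.

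Section 8.7 promises 95% confidence intervals for the response rate but names no method. Clopper-Pearson is named only in the sizing text for Part 1 and Part 2 Stage 1 (Section 8.2 and synopsis), as a one-sided 90% upper bound.

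**The concern.** This is the only hypothesis test that the protocol specifies. It compares a single arm with a fixed historical rate, and Section 8.3 plans no multiplicity adjustment, so the one-sided 0.025 is the only error control in the document. The uncorrected chi-square test relies on a normal approximation to a discrete count. With about 55 subjects its real false-positive probability can lie well above the nominal one. If it does, a borderline result could be declared significant at 0.025 when the actual error rate of the rule is higher, and an exact interval reported beside it could still include 28%.

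**Working it through.** **Inputs** (Sections 8.2 and 8.7): p0 = 0.28, p1 = 0.60, n = 55 (approximate), one-sided alpha 0.025, critical z = 1.960.

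**1. The plan's own figure.** One-sample normal approximation:

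power = Φ[(√n (p1 − p0) − 1.960 √(p0(1 − p0))) / √(p1(1 − p1))]
= Φ[(7.416 × 0.32 − 1.960 × 0.4490) / 0.4899] = Φ(3.05) = 0.9988.

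The statement of at least 90% power is therefore true, with a wide margin.

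**2. Where the uncorrected test rejects at n = 55.** Standard error under the null = √(0.28 × 0.72 / 55) = 0.0605.

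- 21/55 = 38.2%: z = (0.3818 − 0.28) / 0.0605 = 1.68, not rejected.
- 22/55 = 40.0%: z = 0.12 / 0.0605 = 1.98, chi-square 3.93, one-sided p = 0.0237, rejected.

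**3. Exact size and power of each rule at n = 55**, from binomial tail probabilities:

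| Test | Rejects from | P(reject) at 28% | P(reject) at 60% |
|---|---|---|---|
| Chi-square, uncorrected | 22 | 0.0366 | 0.9991 |
| Chi-square, continuity-corrected | 23 | 0.0191 | 0.9979 |
| Exact binomial | 23 | 0.0191 | 0.9979 |

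Relative excess for the uncorrected test: (0.0366 − 0.025) / 0.025 = 46%. The corrected statistic is (0.12 − 1/110) / 0.0605 = 1.83 at 22/55 and 2.13 at 23/55.

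**4. Sensitivity to n.** I take 50 to 60 as a reasonable range for an approximate 55 (my assumption):

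| n | Uncorrected: rejects from | Size | Exact: rejects from | Size |
|---|---|---|---|---|
| 50 | 21 | 0.0232 | 21 | 0.0232 |
| 51 | 21 | 0.0293 | 22 | 0.0146 |
| 52 | 21 | 0.0365 | 22 | 0.0187 |
| 53 | 22 | 0.0237 | 22 | 0.0237 |
| 54 | 22 | 0.0296 | 23 | 0.0150 |
| 55 | 22 | 0.0366 | 23 | 0.0191 |
| 56 | 23 | 0.0240 | 23 | 0.0240 |
| 57 | 23 | 0.0299 | 24 | 0.0154 |
| 58 | 23 | 0.0367 | 24 | 0.0195 |
| 59 | 24 | 0.0243 | 24 | 0.0243 |
| 60 | 24 | 0.0300 | 25 | 0.0158 |

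The uncorrected test exceeds 0.025 at 51, 52, 54, 55, 57, 58 and 60, which is 7 of 11 values. The exact test exceeds it at none.

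**5. Agreement with a 95% interval at n = 55.** Clopper-Pearson gives 27.0% to 54.1% at 22/55, which contains 28%, and 28.7% to 55.9% at 23/55, which does not. At 22/55 the Wilson lower limit is 28.1% (agrees with the uncorrected test) and the Wald lower limit is 27.05% (disagrees).

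**6. How often the choice matters at n = 55.** The two rules differ only at exactly 22 responders. That outcome has probability 0.0366 − 0.0191 = 0.0175 at 28%, and 0.9991 − 0.9979, about 0.001, at 60%.

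**The case against.** A large-sample test at a nominal level is a conventional choice, and its behaviour with a discrete count is well known. Four points on this side carry weight.

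- **The variant is not stated.** A continuity-corrected chi-square gives the same rule as the exact test at 55 subjects and holds the level. A reader might infer that the test's size is 0.0366 without qualification. The text supports that only on the plain, uncorrected reading.
- **The sample size is not fixed.** At 50, 53, 56 or 59 subjects the uncorrected test stays below 0.025. The value at 55 is near the top of the range.
- **The interval method is open.** A reader might infer that the protocol's test and interval contradict each other. Section 8.7 does not support this: it names no interval method, the Clopper-Pearson bounds in Section 8.2 serve a different purpose at a different level, and a Wilson interval would agree with the uncorrected test. An interval method may properly be left to the SAP.
- **No arithmetic in the protocol is wrong.** A reader might take the finding as an error in the power statement, but that statement is correct.

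What remains is that the protocol itself names the test, null and level, and on their ordinary reading they do not agree at the planned size or at most nearby sizes. Power gives no reason to accept this, since it is above 99% at 55 subjects with either rule.

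**Conclusion.** The concern holds in conditional form. As an uncorrected one-sample chi-square test, the Stage 2 primary test has an exact size of 0.0366 at 55 subjects against the stated 0.025, and it exceeds 0.025 at most sample sizes from 50 to 60. If the 95% interval is Clopper-Pearson, 22 of 55 responders would give a rejection alongside an interval that contains 28%; this part depends on a method that Section 8.7 does not name.

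The practical reach is small: one outcome at 55 subjects, and an unlikely one if the true rate is near 60%. It is a should-fix on choice of method. It matters because the choice of test version is not credible once a borderline count has been seen.

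**What to change.** In the synopsis, Section 8.2 and Section 8.7, replace the chi-square test with a one-sided exact binomial test of 0.28 at 0.025, applied at the realised number of subjects in the Stage 2 primary analysis. In Section 8.7, name the two-sided 95% Clopper-Pearson interval for the response rate, so that test and interval agree.

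Give 23/55 (41.8%; size 0.0191, power about 99.8% at 60%) only as the boundary at the planned size. It should not be a fixed success count, because the exact boundary moves with n: it is 22 at 53 subjects and 24 at 57.

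The cost is about one sentence in each of the three places and about 0.1 percentage point of power at 55 subjects (99.9% to 99.8%). The change should be made before Stage 2 response data are analysed.
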